6.2 Secondary end points

In addition to this, several secondary endpoints will be evaluated:

- Comparison between the “TNFi induction” group and the “csDMARD Step-up” group regarding:
 - o Achievement of “sustained clinical remission” at week 24 (and week 36 for the patients remaining on blinded study medication).
 - o Improvement from baseline to week 12 and 24 in individual clinical assessments (78-Tender Joint Count, 76-Swollen Joint Count, Dactylitis Count, SPARCC Enthesitis Score) and composite scores (ASDAS: Axial Spondyloarthritis Disease Activity Score).

- Improvement from baseline to week 12 and 24 in patient-reported outcomes (Patient global assessment of disease activity and pain, BASDAI, BASFI, ASAS Health Index).
- Improvement from baseline to week 12 and 24 in inflammatory parameters (ESR, CRP).
- Changes in concomitant NSAID intake (NSAID-index) and “escape” intra-articular glucocorticoid injections between baseline and week 24
- Difference in occurrence of (serious) adverse events (AEs) and AEs of specific interest between the 2 treatment strategies from baseline to week 24 (and week 36 for patients remaining on blinded study medication). Descriptive analysis of the number and type of adverse events between both strategies
- Percentage of patients achieving (sustained) clinical remission with open-label golimumab treatment after failure of the initial randomized, blinded treatment strategy.
- Exploration of difference in percentage of patients that reach (sustained) clinical remission according to symptom duration (<3 months versus ≥3 month and <12 months). The interaction between treatment group and symptom duration as a continuous predictor will also be analyzed to investigate the effect of symptom duration with regard to reaching the specified primary and secondary outcomes.
- For patients in SPARTACUS Phase B (drug-free remission period):
 - Exploration of the duration of drug-free remission.
 - Time to (documented) pSpA disease flare.
 - Time to restart of “standard-of-care” pSpA treatment.
 - Exploration of clinical parameters that could be predictive for reaching (sustained) clinical remission and/or flare.
- Correlation between the “Patient Acceptable Signs & Symptoms Improvement” (“PASSI”) and different clinical assessments, laboratory values and patient-reported outcomes (or combinations thereof).

7 Trial Design - The present study

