11.3 Measures taken to minimise bias

11.3.1 Randomisation/Blinding/Deblinding

All patients (n=97) will be randomized (1:1) to either immediately receiving golimumab monotherapy (n=48) (the “TNFi-induction”-group), or to the step-up regimen with csDMARDs (n=47) (“csDMARD-Step-up”-group) in a double-blind, double-dummy design.

The “TNFi-induction”-group will receive the standard golimumab dose of 50 mg subcutaneously (SC) every 4 weeks (with matching csDMARD-placebo capsules).

In the “csDMARD-Step-up” regimen, patients will start with oral methotrexate (MTX) capsules at a weekly dose of 15 mg for 4 weeks (with matching “golimumab”-placebo injections). In case of intolerance or toxicity to MTX or MTX placebo, the weekly dose of MTX or MTX placebo can be tapered to 10 mg at week 4, with a further possible reduction to 7,5 mg at week 8; in case of persistent intolerance/toxicity, MTX or MTX placebo will be stopped at week 12. When there are no tolerability/toxicity issues, the weekly dose of MTX or MTX placebo will be increased to 20 mg at week 4 (with an option to again reduce the dose in case of intolerance/toxicity).

At week 12, “Patient Acceptable Signs & Symptoms Improvement” (“PASSI”) will be assessed (see Addendum 3) in order to determine the need for additional, open-label “escape” csDMARD treatment: in case of an acceptable improvement, blinded study medication will be continued until week 24; if there is no satisfactory response, oral sulphasalazine can be added to the blinded study medication at a dose of 2 g per day (escape medication).

The randomization to either the “TNFi induction”-group or the “csDMARD Step-up”-group will be done at the UZ Ghent Pharmacy and the randomization list will be kept there. If according to the data entered in the eCRF, the patient is eligible for randomization, the RedCap system will send a notification to the coordinating study team. Upon review of the screening visit data (including in- and exclusion criteria), the coordinating study team will approve randomization in the eCRF. This will trigger communication with the UZ Ghent pharmacy who will randomize the patient. The local site will be informed via an email and the eCRF system. The UZ Ghent Pharmacy will assemble patient-specific medication kits that will contain (according to the randomization list) the golimumab/placebo syringes for each individual patient. When a new patient is to be randomized, the kits will be sent to the site containing:

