- Psoriasis skin evaluation (if applicable).
- Physician global assessment of disease activity (0-10 numerical rating scale).
- Laboratory investigation:
 - Disease activity: ESR, CRP.
 - Safety: peripheral blood count, serum creatinine, liver function tests (ALT).
 - Research samples (only 10ml serum if treated in UZ Ghent or UZ Leuven)
- Dispensation of study drug and treatment schedule education:
 - Administration of Golimumab/Placebo injection at study site.
 - Dispensation of Placebo/Methotrexate capsules for weekly intake at home.
Dose according to tolerance (see Addendum 8).
 - Depending on the response to the “PASSI”-question:
 - “PASSI”-Yes: continuation of blinded study medication
 - “PASSI”-No: prescription of Sulphasalazine open-label escape treatment.

Phase A – Visit 6: WEEK 16 (+/- 1 week)

- Assessment of adverse events.
- Current medication (dose and duration).
- Study drug accountability.
- Patient reported outcomes (see Addendum 7):
 - Patient global assessment of disease activity (0-10 numerical rating scale).
 - Patient global assessment of pain (0-10 numerical rating scale).
 - Bath Ankylosing Spondylitis Disease Activity Index (BASDAI).
- Targeted physical examination.
- Rheumatological examination (see Addendum 5):
 - 78-Tender and 76-swollen joint count.
 - Dactylitis assessment.
 - Enthesitis assessment (SPARCC Enthesitis Index).
- Laboratory investigation:
 - Disease activity: ESR, CRP.
 - Safety: at the discretion of the treating rheumatologist (depending on the use of e.g. sulphasalazine escape medication).
- Dispensation of study drug:
 - Administration of Golimumab/Placebo injection at study site.
 - Dispensation of Placebo/Methotrexate capsules for weekly intake at home.
Dose according to tolerance (see Addendum 8).

Phase A – Visit 7: WEEK 20 (+/- 1 week)

- Assessment of adverse events.
- Current medication (dose and duration).
- Study drug accountability.
- Patient reported outcomes (see Addendum 7):

- Patient global assessment of disease activity (0-10 numerical rating scale).
- Patient global assessment of pain (0-10 numerical rating scale).
- Bath Ankylosing Spondylitis Disease Activity Index (BASDAI).
- Targeted physical examination.
- Rheumatological examination (see Addendum 5):
 - 78-Tender and 76-swollen joint count.
 - Dactylitis assessment.
 - Enthesitis assessment (SPARCC Enthesitis Index).
- Laboratory investigation:
 - Disease activity: ESR, CRP.

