 - Safety: at the discretion of the treating rheumatologist (depending on the use of e.g. sulphasalazine escape medication).
- Dispensation of study drug:
 - Administration of Golimumab/Placebo injection at study site.
 - Dispensation of Placebo/Methotrexate capsules for weekly intake at home.
Dose according to tolerance (see Addendum8).

Phase A – Visit 8: WEEK 24 (+/- 1 week)

- Assessment of adverse events.
- Tuberculosis Questionnaire.
- Current medication (dose and duration).
- Study drug accountability.
- Patient reported outcomes (see Addendum 7):
 - Patient global assessment of disease activity (0-10 numerical rating scale).
 - Patient global assessment of pain (0-10 numerical rating scale).
 - Bath Ankylosing Spondylitis Disease Activity Index (BASDAI).
 - Bath Ankylosing Spondylitis Functional Index (BASFI).
 - Health Assessment Questionnaire (for SpA) (HAQ(-SpA)).
 - Assessment of SpondyloArthritis international Society (ASAS) Health Index (ASAS-HI).
 - “Health Economic Evaluation”: EuroQoL 5 dimensions, co-morbidity Index (SCQ) and healthcare utilization and productivity (in the past 3 months)
- Targeted physical examination.
- Vital signs (blood pressure, heart frequency).
- Weight.
- Smoking/alcohol status
- Rheumatological examination (see Addendum 5):
 - 78-Tender and 76-swollen joint count.
 - Dactylitis assessment.
 - Enthesitis assessment (SPARCC Enthesitis Index).
 - Bath Ankylosing Spondylitis Metrology Index (BASMI), including tragus-to-wall distance, lumbar flexion (Schöber index), lumbar lateroflexion, cervical rotation and intermalleolar distance; chest expansion.
 - Psoriasis skin evaluation (if applicable).
 - Physician global assessment of disease activity (0-10 numerical rating scale).
- Laboratory investigation:
 - Disease activity: ESR, CRP.

- Safety: peripheral blood count, serum creatinine, uric acid, liver function tests (ALT, gamma-GT, Alkaline Phosphatase, LDH), Creatine Kinase.
- Research samples (4 x 8ml blood-CPT and 10ml serum if treated in UZ Ghent or UZ Leuven)
- Trial continuation evaluation based on clinical remission (yes/no) at week 24 and potential sustained clinical remission (at week 12 and 24):
 - No clinical remission: stop blinded study medication; start open-label golimumab 50 mg SC every 4 weeks.
 - Clinical remission (but not sustained remission): continuation of the same blinded study medication.

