	scr	Biopt	W0	W4	W8	W12	W16	W20	W24	W28	W36	W48	W60	
Informed Consent	X													
Inclusion/Exclusion crit	X	X	X											
synovial biopsy & Ultrasound		X												
Anamnesis ^a	X													
Current Medication	X		X	X	X	X	X	X	X	X	X	X	X	X
Adverse Events			X	X	X	X	X	X	X	X	X	X	X	X
Latent TB screening ^b	X					X			X		X	X	X	
Patient disease activity & pain NRS	X		X	X	X	X	X	X	X	X	X	X	X	X
BASDAI			X	X	X	X	X	X	X	X	X	X	X	X
BASFI, ASAS-HI, Health economic evaluations			X			X			X		X	X	X	
HAQ-SpA			X						X			X		
Post biopsy questionnaire		X												
(Targeted) Physical examination ^f	X		X	X	X	X	X	X	X	X	X	X	X	X
Vital Signs	X					X			X		X	X	X	
Length (only at screening), weight	X					X			X		X	X	X	
Smoking/alcohol status	X					X			X		X	X	X	
76SJC/78TJC, dactylitis, enthesitis (SPARCC)	X		X	X	X	X	X	X	X	X	X	X	X	X
BASMI, chest expansion, Psoriasis assessment			X			X			X		X	X	X	X
Physician global NRS	X					X			X		X	X	X	
HLA B27 ^c , anti-CCP AB ^d , HBV ⁱ , HCV ⁱ , HIV ⁱ , CMV IgG ⁱ	X													
Safety Lab tests ^e	X ^e			X	X	X	X	X	X	X	X	X	X	X
ESR, CRP	X		X	X	X	X	X	X	X	X	X	X	X	X
Serum Pregnancy Testing	X													
Research samples ^g		X	X ^h			X			X					
PASSI						X					X	X		
Assessment of clinical remission status						X			X		X	X	X	
Study drug admin/dispensation			X	X	X	X	X	X	X	X	X	X	X	
Study drug accountability				X	X	X	X	X	X	X	X	X	X	

^a Demographic data, symptom duration, medical history, past anti-rheumatic treatment, family history

^b v1A: chest X-ray (if not performed within the last 3 months), TB test (Mantoux PPD-test or Quantiferon), TB questionnaire; other visits: only TB questionnaire

^c If not known

^d if not determined within the last 12 months

^e At v1A (for visit 1A: results of tests performed within the last month are allowed), week 24, week 36, week 48, week 60: peripheral blood count, serum creatinine, uric acid, liver function tests (ALT, GGT, AP, LDH), CK

At week 4, week 12, week 28: peripheral blood count, serum creatinine, ALT

At week 8, week 16, week 20: at the discretion of the treating rheumatologist

At the unscheduled visit: at the discretion of the treating rheumatologist

^f Full physical exam at screening, targeted physical exam at the other visits

^g 4 x 8ml blood-CPT (the synovial biopsy sampling units will also collect 10ml serum; at week 12: only 10ml serum; ZNA Jan Palfijn will only collect serum at BL)

^h Only if no samples taken at visit 1B

ⁱ if not determined within the last 3 months

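### Safety bloods at weeks 16 and 20 depend on sulphasalazine escape, so laboratory-detected adverse events may be found unequally between the strategies

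*Protocol*

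**What the plan says.** Section 11.4.1 and footnote e of the Phase A flow chart fix the safety laboratory tests as follows.

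- **Weeks 4 and 12, all patients:** "At week 4, week 12, week 28: peripheral blood count, serum creatinine, ALT".
- **Week 24, all patients:** a fuller panel, "Safety: peripheral blood count, serum creatinine, uric acid, liver function tests (ALT, gamma-GT, Alkaline Phosphatase, LDH), Creatine Kinase".
- **Weeks 16 and 20:** the visit descriptions say "Safety: at the discretion of the treating rheumatologist (depending on the use of e.g. sulphasalazine escape medication".
- **Flow chart:** footnote e gives discretion without naming sulphasalazine, and includes week 8: "At week 8, week 16, week 20: at the discretion of the treating rheumatologist".

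Escape is decided at week 12. A PASSI answer of no leads to "prescription of Sulphasalazine open-label escape treatment". Sections 10 and 11.3.1 describe it as an addition to the blinded medication, so it is open to both arms.

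Section 6.2, repeated in 13.2, lists as a secondary endpoint "Difference in occurrence of (serious) adverse events (AEs) and AEs of specific interest between the 2 treatment strategies from baseline to week 24", followed by "Descriptive analysis of the number and type of adverse events between both strategies". Neither section distinguishes abnormalities found at fixed draws from those found only because a discretionary test was done.

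**The concern.** A symptomless cytopenia or rise in ALT is found only if the test is done. At weeks 16 and 20 the protocol links the test to a treatment that starts after randomisation, depends on the patient's judgement of response and side effects, and is open-label, so the rheumatologist knows who takes it. If more patients in one arm take sulphasalazine, that arm may be tested more often and may show more laboratory adverse events even when true risk is equal.

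The trial's own hypothesis makes unequal escape plausible: section 13.1 assumes 20% remission with methotrexate against 50% with golimumab. If PASSI follows the same pattern, escape and the extra testing would be more common in the step-up arm, and the distortion would favour golimumab.

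The affected findings matter for this comparison. Section 9.5.8 lists raised liver enzymes as very common and low white-cell and platelet counts as common with methotrexate. Section 9.2.8 lists liver problems and low blood counts for golimumab.

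**Working it through.** **The plan's own figures.** The protocol gives no escape rate, testing rate or laboratory adverse event rate, so there is no stated figure to reproduce on this point. Its one design figure is 45 per group for at least 80% power (20% v 50%, alpha 5%, Fisher's exact test). Exact enumeration of the two-sided test gives 81.5%. That figure concerns the primary endpoint and is not in question.

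**Inputs from the protocol.** Three post-baseline safety draws to week 24 are fixed for all (weeks 4, 12, 24). Two may depend on escape (weeks 16, 20). There are 45 patients per arm. Week 8 is left out: it is discretionary, but it precedes escape and is not tied to it.

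**Assumptions, none from the protocol.** P is the share of an arm on sulphasalazine. As a worst case, every escape user and nobody else has safety tests at weeks 16 and 20. Each draw carries the same independent chance q = 5% of a transient abnormality in both arms.

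**Formulas.**
- Mean safety draws per patient = 3 + 2P.
- Share with at least one abnormality detected = 1 − [(1 − P) × 0.95³ + P × 0.95⁵], with 0.95³ = 0.8574 and 0.95⁵ = 0.7738.
- Difference between arms = (P₁ − P₂) × (0.8574 − 0.7738) = 0.0836 × (P₁ − P₂). Per 45 patients this is 3.76 × (P₁ − P₂).

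| Escape, step-up / golimumab | Mean draws | Detected | Difference | Extra patients per 45 |
|---|---|---|---|---|
| 30% / 30% | 3.6 v 3.6 | 16.8% v 16.8% | 0 | 0 |
| 40% / 30% | 3.8 v 3.6 | 17.6% v 16.8% | 0.8 points | 0.4 |
| 50% / 20% | 4.0 v 3.4 | 18.4% v 15.9% | 2.5 points | 1.1 |
| 60% / 10% | 4.2 v 3.2 | 19.3% v 15.1% | 4.2 points | 1.9 |

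**Sensitivity to the assumptions.**
- *Risk per draw of 10%:* the multiplier becomes 45 × (0.9³ − 0.9⁵) = 45 × (0.7290 − 0.5905) = 6.23. The three unequal splits then give 0.6, 1.9 and 3.1 extra patients.
- *Partial testing:* let 80% of escape users and 50% of other patients be tested at each of the two visits. At 60% v 20% escape the excess is 0.45 patients (q = 5%) or 0.74 (q = 10%). Under worst-case testing the same split gives 1.5 or 2.5.
- *Extreme split of 80% v 10%, worst-case testing:* 2.6 (q = 5%) or 4.4 (q = 10%).
- *Equal testing of escape users and others, or comparison on the fixed draws only:* zero at any escape rates.

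**The case against.** The strongest case against the point has four parts.

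- **Narrow reach.** Weeks 12 and 24 are fixed for all. Adverse events are assessed at every visit in both arms. Everyone already gives blood for ESR and CRP at weeks 16 and 20, so only the added safety panel varies. An abnormality lasting to week 24 is found in both arms, and section 15.4 asks for relevant adverse events, not every abnormal value. All of this stands, and it limits the exposure largely to transient laboratory abnormalities between weeks 12 and 24.
- **Discretion is not a rule.** Sulphasalazine is given as an example, and the flow-chart footnote omits it. Every patient takes blinded methotrexate or placebo, so a blinded rheumatologist has reason to test other patients too. This stands, which is why full dependence on escape is a worst case.
- **Sulphasalazine toxicity belongs to the strategy.** Section 5.1 defines the step-up approach as including sulphasalazine, so adverse events it causes are a real difference between strategies. This stands and rules out replacing the full comparison with fixed draws alone.
- **It is analysis-plan detail.** Handling unscheduled laboratory findings is commonly left to the analysis plan, which is not at hand. This stands in part. The unequal collection rule is nevertheless in the protocol, beside an endpoint covering the whole window, and no later plan can recover tests that were not done.

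A reader might infer that the whole safety comparison is biased towards golimumab from week 12 onward. The protocol does not support that. It gives no escape rates, and section 13.1 says there are no remission data under methotrexate. PASSI weighs side effects as well as benefit, so even the direction is a plausible expectation and not a fact.

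**Conclusion.** The point holds in a limited form. The protocol makes safety testing at weeks 16 and 20 depend on a post-randomisation, response-related treatment, and it compares adverse events between strategies over a window that includes those visits. If escape differs by arm and testing follows it, laboratory-detected adverse events can be counted unequally at equal true risk.

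The likely size is small: about 0.4 to 1.9 patients per 45 under worst-case testing, a 5% risk per draw and escape splits from 40/30 to 60/10. Partial testing makes it smaller; a higher risk per draw or a more extreme split makes it larger. The comparison is secondary and descriptive. The primary endpoint rests on clinical examination for arthritis, dactylitis and enthesitis, so neither it nor the power is affected.

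**What to change.** In sections 6.2 and 13.2:

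1. Keep the full adverse event comparison to week 24, with sulphasalazine toxicity counted as part of the strategy.
2. Add a comparison of laboratory-detected adverse events restricted to the draws mandatory for all patients (weeks 4, 12 and 24).
3. Flag abnormalities found only at discretionary draws.
4. Report the number of safety draws per arm.

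If the analysis plan already does this, only the wording of the two sections needs aligning. No change to the monitoring schedule is proposed.

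The cost is one more table and a flag for the draw at which each abnormality was found. The restricted comparison is less sensitive to transient abnormalities between weeks 12 and 24, but these remain in the full table.

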14.1 Method of data collection

An electronic data capture (EDC) system, i.e. REDCap, will be used for data collection. REDCap is provided and maintained by Vanderbilt University; a license for use was granted to the Health, Innovation and Research Institute (HIRUZ). REDCap is a web-based system.

14.1.1 Case Report Form (CRF)

Only the data required by the protocol are captured in the eCRF. The eCRFs and the database will be developed, based on the protocol. The final eCRF design will be approved by the CI.

The study site staff is responsible for data entry in REDCap.

Subjects that are included in the trial, will be assigned a unique study number upon their registration in REDCap. On all documents submitted to the sponsor or CI, subjects will be pseudonomised. REDCap has built-in options for univariate alerts, such as valid-value, valid-range, and missing-value alerts.

Data reported on each eCRF should be consistent with the source data. If information is not known, this must be clearly indicated on the eCRF. All missing and ambiguous data will be clarified.

All data entries and corrections will only be performed by study site staff, authorised by the Investigator. Data will be reviewed by trained personnel (monitor, data manager) and any errors or inconsistencies will be clarified.

14.1.2 Data directly collected in the eCRF (no source available)

For this trial, we use ePRO's where the participants complete surveys in the hospital on a tablet of the hospital and connected to a secured hospital network. The ePRO can be opened by using a survey link that is unique per participant and per visit.

The participant will need to log in to the survey before he/she can complete the survey.

14.2 Data storage

The data is accessed through a web browser directly on the secure REDCap server. The server is hosted within the Ghent University Hospital campus and meets hospital level security and back-up requirements.

Privacy and data integrity between the user's browser and the server is provided by mandatory use of Transport Layer Security (TLS), and a server certificate issued by TERENA (Trans-European Research and Education Networking Association). All trial sites will have access to REDCap. Site access is controlled with IP restriction.

14.3 Archiving of data

The investigator and sponsor specific essential documents will be retained for at least 25 years. At that moment, it will be judged whether it is necessary to retain them for a longer period, according to applicable regulatory or other requirements.

Once all subjects have completed the study visits and the study was closed the study documents will be archived. Documents will be stored at MERAk N.V. BELGIE [name] - [contact]

14.4 Access to data

The investigators and institutions involved in the trial will permit clinical trial-related monitoring, audits and regulatory inspections (including provision of direct access to source data and documents).

Login in REDCap is password controlled. Each user will receive a personal login name and password and will have a specific role which has predefined restrictions on what is allowed in REDCap. Furthermore, users will only be able to see data of subjects of their own site. Any activity in the software is traced and transparent via the audit trail.

15 Safety

15.1 Definitions

Adverse Events and Adverse Reactions	
Term	Definition
Adverse Event (AE)	Any untoward medical occurrence in a subject to whom a medicinal product is administered and which does not necessarily have a causal relationship with this treatment.
Unexpected Adverse Event	An adverse event of which the nature or severity is not consistent with the Reference Safety Information (RSI) of the product (i.e. the applicable information in the Investigator's Brochure (IB) for an investigational medicinal product which is not authorised or in the Summary of Product Characteristics (SmPC) for an authorised investigational medicinal product).
Adverse Reaction (AR)	An untoward and unintended response in a subject to an investigational medicinal product which is related to any dose administered to that subject. The phrase "response to an investigational medicinal product" means that a causal relationship between a study medication and an AE is at least a reasonable possibility, i.e. the relationship cannot be ruled out. All cases judged by either the reporting medically qualified professional or the Sponsor as having a reasonable suspected causal relationship to the study medication qualify as adverse reactions.
Serious Adverse Event (SAE)	
Any untoward medical occurrence that:
 
 • requires inpatient hospitalisation or prolongation of existing hospitalisation; • results in persistent or significant disability/incapacity; • results in a congenital anomaly or birth defect; • is life-threatening; or • results in death. 
Other important medical events may also be considered serious if they jeopardise the subject or require an intervention to prevent one of the above consequences.
 
NOTE: The term "life-threatening" in the definition of "serious" refers to an event in which the subject was at risk of death at the time of the event; it does not refer to an event which hypothetically might have caused death if it were more severe.

Suspected Unexpected Serious Adverse Reaction (SUSAR)	A serious adverse reaction, the nature, severity or outcome of which is not consistent with the Reference Safety Information (RSI).

NB: to avoid confusion or misunderstanding of the difference between the terms “serious” and “severe”, the following note of clarification is provided: “Severe” is often used to describe intensity of a specific event, which may be of relatively minor medical significance. “Seriousness” is the regulatory definition supplied above.

Attributions	
Term	Definition
Not related	An adverse event which is not related to the use of the drug.
Unlikely related	An adverse event for which an alternative explanation is more likely - e.g. concomitant drug(s), concomitant disease(s), and/or the relationship in time suggests that a causal relationship is unlikely.
Possibly related	An adverse event which might be due to the use of the drug. An alternative explanation - e.g. concomitant drug(s) or concomitant disease(s) - is inconclusive. The relationship in time is reasonable; therefore the causal relationship cannot be excluded.
Probably related	An adverse event which might be due to the use of the drug. The relationship in time is suggestive (e.g. confirmed by dechallenge). An alternative explanation is less likely - e.g. concomitant drug(s) or concomitant disease(s).
Definitely related	An adverse event which is listed as a possible adverse reaction and cannot be reasonably explained by an alternative explanation - e.g. concomitant drug(s) or concomitant disease(s). The relationship in time is very suggestive (e.g. it is confirmed by dechallenge and rechallenge).

An adverse event is considered associated with the use of the drug if the attribution is ‘possibly’, ‘probably’ or ‘definitely related’.

